Recently, there have been multiple prospective clinical trials exploring the effect metformin has in non-diabetic patients. Non-diabetic patients were treated with 250mg - 875mg three times daily or 2000mg daily for 14 days – 48 weeks showing an excellent safety profile. The metformin was very well tolerated with the primary side effect (30-60% of subjects) being self-limited gastrointestinal discomfort including mild diarrhea and anorexia.²³⁻²⁵ Across multiple disease states, metformin has been shown to decrease appetite stimulating GLP-1, decrease low density lipid profiles, decrease the mitotic rate in breast cancer, and improve liver pathology in patients with non-alcoholic steotatic hepatitis.^{1,12,20,23,25,26} As discussed above, some of these changes are attributed to the anti-glycemic and anti-tumor effects of metformin, yet the anti-inflammatory role cannot be underestimated. To our knowledge, there has been no study of the affect metformin has on inflammation, the microbiome, thrombosis, and cellular respiration as it links to physiologic and cognitive changes in non-diabetic patients.

Therefore, we hypothesize that aged non-diabetic subjects treated with a short course of metformin will have a beneficial change in metabolic and immune signaling and gut microbial homeostasis with an improved inflammatory response.

Study Objectives

This is a study examine if metformin improves the immune and inflammatory responses of non-diabetic, older adults.

We will begin to test this hypothesis by examining the following specific aims.

1. To determine the influence of metformin on basic metabolic, coagulation, and hematologic profiles

2. To discover the influence of metformin on physiologic and inflammatory responses in older adults including affects on peripheral blood mononuclear cells (PBMCs) phenotype and ex vivo inflammatory response to innate immune stimuli.
3. To discover the influence of metformin on thrombotic factors and platelet function in an ex vivo model.
4. To determine the influence of metformin on cellular respiration pathways including epigenetics and mitochondrial function.
5. Determine the influence of metformin on physiologic parameters of physical activity including grip strength as measured by a dynamometer and a short physical performance battery.
6. To establish dose specific gastrointestinal changes to the microbiome of metformin.

Study Design & Methods

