All samples will be gathered prior to, throughout the 90 days (30, 60 and 90 days), and again approximately 30 days following completion of the metformin exposure.

- 1.) Changes in basic metabolic, coagulation, and hematologic profiles during and following exposure to metformin.
- 2.) Establish dose specific responses to affects on PBMC and ex vivo inflammatory response to innate immune system during and following metformin exposure. Cells will also be assessed for epigenetic changes by Chromatin immunoprecipitation.
- 3.) Understand the dose-specific effects of metformin on thrombotic factors, coagulation, and platelet function in an ex vivo model.
- 4.) Mitochondrial analysis of cellular respiration.
- 5.) Stool samples assessed for changes in the gastrointestinal microbiome

Cognition and physiology will be assessed at the baseline, 90 day, and 120 day time points.

- 6.) Physiologic testing: grip strength as measured by a dynamometer and a short physical performance battery

Unexpected adverse events including significant illness, hospitalization, emergent or urgent surgery or procedure, psychiatric hospitalization or inpatient rehabilitation, would require the study team to discontinue the subject's participation.

Additionally, if the subject fails to participate in the required study procedures they will receive compensation for those items that they have completed. However, they may be removed from the study and not allowed to participate in the study going forward. If participation needs to be discontinued, the study team will make up to 1-5 separate efforts to contact the subject in order to discuss their removal from the study and to instruct them to both discontinue and return the study medication. All unused study medication will be returned to the study pharmacy, IDS.

Eligibility Criteria

List the inclusion criteria:

1. Age ≥ 55 and ≤ 85 years of age
2. Non-diabetic
3. Adjusted risk analysis index (RAI) 20-42
4. Estimated glomerular filtration rate ≥ 45
5. No evidence of hepatic dysfunction on comprehensive metabolic panel
6. No clinical evidence of cardiac failure
7. Existing University of Pittsburgh Medical Center Patients

List the exclusion criteria:

1. Hypersensitivity to metformin or any component of the formulation
2. Acute or chronic metabolic acidosis with or without coma
3. Pregnant or breastfeeding females
4. Evidence or history of hepatic, renal, or cardiac failure
5. Excessive acute or chronic ethanol use

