6. Planned or known hospital admission, exposure to anesthesia, or surgical intervention 30 days prior to study or scheduled 30 days after the trial initiation
7. Laboratory analysis showing HbA1c > 6.1 or eGFR < 45 on baseline labs

Statistical Considerations

This prospective randomized control study is powered based upon prior studies our group has completed on the cellular response to inflammation from PBMCs in healthy volunteers. This variable was chosen, as we believe this to be the most impactful variable included in this study. Previously, our group has looked at the immune response to lipopolysaccharide in healthy volunteers PBMCs ex vivo. In this study, we noted a statistically significant increase in pro-inflammatory cytokines between the two groups by approximately 40%. We expect a standard deviation of around 50% of the baseline values. Therefore, based upon previous inflammatory changes seen in healthy volunteers and a desired alpha = 0.05 and a beta = 0.2, our most conservative projected sample size using a two-sided Mann-Whitney test is 25 patients per group. With possible attrition we plan to enroll 30 patients per group. Therefore, across dosing we require a total of 120 patients in order to reach statistical significance. For this trial, we are collecting data in order to pilot a larger trial after we have data from this trial. Therefore, we expect to use the data from these 32 patients to understand how to power a larger study.

Patients will be used as their own controls before, during and after the exposure period, allowing for paired testing. Changes in laboratory venous and stool samples values will be compared using parametric and non-parametric standard statistics, as required. Differences in baseline physiologic testing will be controlled for based on their RAI score and the medical comorbidities, therefore each person serves as their own control. Both the 90 day treatment results and the 120 day test results (30 days after treatment discontinuation) for physiologic

testing will be compared to the individuals baseline values. Additionally, the various treatment doses will be compared at baseline, to ensure randomization allowed for equivalent patient groupings.

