Randomization and blinding will be completed by IDS who will be provided with a block randomization scheme (see Sample Randomization in the Supporting Documents Section). The randomization scheme will have a block size of 8. Within each block, the randomization is classic and 1:1:1:1 between groups.

Changes from baseline will be investigated at each time point using ANOVA. Significance will be assumed with $p<0.05$.

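### The p<0.05 rule for ANOVA at each time point is tied to no endpoint, visit or contrast, and the PBMC lead variable does not fix a single test

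*Combined protocol and SAP*

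**What the plan says.** The decision rule closes the Statistical Considerations section of the combined protocol and SAP: "Changes from baseline will be investigated at each time point using ANOVA", and then "Significance will be assumed with $p<0.05". The ANOVA factor is not stated. No analysis is labelled primary, secondary or exploratory, and there is no multiplicity adjustment or test hierarchy.

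Earlier in the same section the trial is sized on the PBMC inflammatory response: "This variable was chosen, as we believe this to be the most impactful variable included in this study". The effect comes from an earlier study in which "we noted a statistically significant increase in pro-inflammatory cytokines between the two groups by approximately 40" per cent. The standard deviation is put at about 50% of baseline, and a two-sided Mann-Whitney test at alpha 0.05 and beta 0.2 gives 25 per group. That becomes 30 per group with attrition and 120 over four groups. The section then says that this trial's 32 patients serve to learn how to power a larger study. It also allows paired testing, leaves laboratory and stool changes to parametric or non-parametric methods as needed, and compares physical results at days 90 and 120 with each person's own baseline.

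Study Design & Methods numbers five sample-based domains, with post-baseline samples at days 30, 60 and 90 and about 30 days after exposure ends. For function, "Cognition and physiology will be assessed at the baseline, 90 day, and 120 day time points". The PBMC item reads: "Establish dose specific responses to affects on PBMC and ex vivo inflammatory response to innate immune system during and following metformin exposure". The matching aim in Study Objectives covers PBMC "phenotype and ex vivo inflammatory response to innate immune stimuli".

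**The concern.** The alpha of 0.05 in the sample size calculation describes one two-group test. The decision rule permits many tests, each at 0.05. Even within the lead variable, a reader of the results could not tell which PBMC finding was planned: any pro-inflammatory cytokine, any of four visits, any comparison among four arms, by ANOVA, a paired test or another standard test.

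The rule is a positive statement about what will be called significant, so the problem is more than missing detail. It also bears on the pilot's own purpose. A result singled out because it crossed p<0.05 at 8 per arm will tend to overstate the effect, and a larger study powered on it would be too small.

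**Working it through.** **1. The plan's own figure.** Inputs from Statistical Considerations: difference 40%, SD 50%, two-sided alpha 0.05, power 0.80.

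n per group = 2 × [(1.960 + 0.842) × 0.5 / 0.4]² = 24.5, so 25. This reproduces the stated 25. A t-test version, or a Mann-Whitney correction for normal data (24.5 ÷ (3/π) = 25.7), gives 26, which is close enough. Then 25 / (1 − 1/6) = 30, and 30 × 4 = 120. The arithmetic is sound for one two-group comparison.

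**2. Arm size in this trial.** 32 patients at 1:1:1:1 gives 32 / 4 = 8 per arm.

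**3. One measure, four visits.** Assumption: the ANOVA factor is dose arm, as the dose-specific wording of the PBMC item suggests.

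- If the four tests were independent: 1 − 0.95⁴ = 18.5%.
- They share a baseline. With equal correlation ρ between time points, each change has variance 2σ²(1 − ρ), and two changes have covariance σ²(1 − ρ). The changes therefore correlate at 0.5 whatever ρ is.
- Null simulation of a four-arm F test on change, 8 per arm, 40,000 runs: 16.0%, 16.0% and 16.1% for ρ = 0.3, 0.5 and 0.7.
- At 30 per arm (20,000 runs): 16%. Sample size does not alter it.

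**4. More measures (illustrative, because the plan does not state how many there are).**

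| Set of tests, 8 per arm | Assumed correlation between measures | Chance of at least one p<0.05 |
|---|---|---|
| 3 cytokines × 4 visits | 0.8 to 0 | 31-41% |
| 5 cytokines × 4 visits | 0.8 to 0 | 39-59% |
| One measure per domain: 5 × 4 + 1 × 2 = 22 tests | 0.8 / 0.5 / 0 | about 40% / 54% / 63% |

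At 30 per arm the 22-test figure is 38-63%. The expected number of false positives among 22 tests is 22 × 0.05 = 1.1, whatever the correlation. Cognition is scheduled at two post-baseline visits but is not in this count.

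**5. Power of one fixed contrast.** The standardised effect is 40 / 50 = 0.8. If 50% is the SD of raw values, the effect on the change scale is d = 0.8 / √(2(1 − ρ)), that is 0.676, 0.800 and 1.033 for ρ = 0.3, 0.5 and 0.7. If 50% is already the SD of change, d = 0.8, the same as the ρ = 0.5 column. The pairwise test in a four-arm model has noncentrality d√(n/2) on 4(n − 1) degrees of freedom.

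| Evaluable per arm | ρ = 0.3 | ρ = 0.5 | ρ = 0.7 |
|---|---|---|---|
| 8 (28 df) | 25.7% | 33.9% | 51.4% |
| 7 (24 df) | 22.9% | 30.1% | 45.8% |
| 6 (20 df) | 20.0% | 26.1% | 39.9% |

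The plan's own attrition allowance (30 down to 25) would leave 8 × 25/30 = 6.7 per arm, so the lower rows matter.

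**The case against.** The strongest reply is that this is a pilot. The title says so, the aims speak of discovering and of beginning to test a hypothesis, and the sample size text separates the 120 patients needed to reach significance from the 32 in this trial. The alpha of 0.05 belongs to the calculation behind the 120, and the documents make no confirmatory claim. This stands as to weight, and it is why the point is moderate. It does not remove the defect, because nowhere are p-values called descriptive and the significance rule is kept.

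A reader might infer that the plan applies ANOVA at p<0.05 to every endpoint. The text does not say that. The rule is simply unrestricted, and the same section plans paired and other tests. Those extra routes add tests rather than remove any.

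A reader might also subdivide the domains into many more tests and conclude that a false claim from the trial as a whole is very likely. The documents do not support a particular count. They do not list the measures, the domains belong to separate aims, and nothing says that a finding in any one domain makes the trial positive. Even the 22-test figure is only an illustration.

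Finally, the ANOVA factor might be time rather than dose arm, given the emphasis on patients as their own controls. The simulated rates would not then carry over unchanged.

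**Conclusion.** The point holds, at moderate weight. The significance rule is open-ended, and the lead variable does not identify one test. The firmest figure is about 16% for one PBMC measure over four visits. It needs no assumed number of endpoints and does not depend on arm size, but it does assume dose arm as the ANOVA factor and equal correlation over time. The 31-59% for several cytokines and 40-63% for 22 tests rest further on assumed counts and correlations, and show direction and scale only.

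Two stronger conclusions do not follow. The 25 per group is not miscalculated: it reproduces for a single two-group test. And the plan does not present itself as confirmatory, so this is not a failure to control error in a pivotal trial.

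**What to change.** Replace the blanket p<0.05 rule with one of two statements.

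- **One lead comparison.** Name one PBMC cytokine response, one visit and one between-arm contrast, with its test and the ANOVA factor, all chosen by the sponsor. Make this the only test at two-sided 0.05. State its power for a 0.8 SD contrast: about 26-51% with all 8 per arm evaluable, and about 20-40% with 6 evaluable per arm (correlation over time 0.3-0.7).
- **No formal test.** State that all p-values in this pilot are descriptive.

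Under either option, report all other endpoints and visits as exploratory estimates with 95% confidence intervals, which serve the stated aim of planning a larger study.

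The cost is a change of wording, with no extra patients, visits or assays. Fewer results can be called significant, and a lead test, if kept, may well be non-significant even if the planned effect is real.
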